5.3.5.12 Cases of Accidental Overdose or Medication Error

Accidental overdose and medication error (hereafter collectively referred to as "special situations"), are defined as follows:

- Accidental overdose: accidental administration of a drug in a quantity that is higher than the assigned dose
- Medication error: accidental deviation in the administration of a drug In some cases, a medication error may be intercepted prior to administration of the drug.

Special situations are not in themselves adverse events, but may result in adverse events. Each adverse event associated with a special situation should be recorded separately on the Adverse Event eCRF. If the associated adverse event fulfils seriousness criteria *or qualifies as an adverse event of special interest*, the event should be reported to the Sponsor immediately (i.e., no more than 24 hours after learning of the event; see .Section 5.4.2.).

For ocrelizumab, adverse events associated with special situations should be recorded as described below for each situation:

Ocrelizumab—F. Hoffmann-La Roche Ltd 79/Protocol MA30143, Version 10.0

- Accidental overdose: Enter the adverse event term. Check the "Accidental overdose" and "Medication error" boxes.
- Medication error that does not qualify as an overdose: Enter the adverse event term. Check the "Medication error" box.
- Medication error that qualifies as an overdose: Enter the adverse event term. Check the "Accidental overdose" and "Medication error" boxes.

In addition, all special situations associated with ocrelizumab, regardless of whether they result in an adverse event, should be recorded on the Adverse Event eCRF as described below:

- Accidental overdose: Enter the drug name and "accidental overdose" as the event term. Check the "Accidental overdose" and "Medication error" boxes.
- Medication error that does not qualify as an overdose: Enter the name of the drug administered and a description of the error (e.g., wrong dose administered, wrong dosing schedule, incorrect route of administration, wrong drug, expired drug administered) as the event term. Check the "Medication error" box.
- Medication error that qualifies as an overdose: Enter the drug name and "accidental overdose" as the event term. Check the "Accidental overdose" and "Medication error" boxes. Enter a description of the error in the additional case details.
- Intercepted medication error: Enter the drug name and "intercepted medication error" as the event term. Check the "Medication error" box. Enter a description of the error in the additional case details.

As an example, an accidental overdose that resulted in a headache would require two entries on the Adverse Event eCRF, one entry to report the accidental overdose and one entry to report the headache. The "Accidental overdose" and "Medication error" boxes would need to be checked for both entries.

Adverse events associated with an overdose of ocrelizumab in previous clinical studies include IRRs and infection.

5.3.5.13 Patient-Reported Outcome Data

Adverse event reports will not be derived from PRO data by the Sponsor and safety analyses will not be performed using PRO data. Sites are not expected to review the PRO data for adverse events.

Please note that the methods for collecting and analyzing PRO data are different from those for the ascertainment of observed or volunteered adverse events. Due to these differences, PRO data will not be reported as adverse events and no attempt will be made to resolve any noticeable discrepancies between PRO data and observed or volunteered adverse events.

5.4 IMMEDIATE REPORTING REQUIREMENTS FROM INVESTIGATOR TO SPONSOR

Certain events require immediate reporting to allow the Sponsor to take appropriate measures to address potential new risks in a clinical trial. The investigator must report such events to the Sponsor immediately; under no circumstances should reporting take place more than 24 hours after the investigator learns of the event. The following is a list of events that the investigator must report to the Sponsor within 24 hours after learning of the event, regardless of relationship to study drug:

- Serious adverse events (defined in Section 5.2.2; see Section 5.4.2 for details on reporting requirements)
- Adverse events of special interest (defined in Section 5.2.3; see Section 5.4.2 for details on reporting requirements)
- Pregnancies (see Section 5.4.3 for details on reporting requirements)

For serious adverse events and adverse events of special interest, the investigator must report new significant follow-up information for these events to the Sponsor immediately (i.e., no more than 24 hours after becoming aware of the information). New significant information includes the following:

- New signs or symptoms or a change in the diagnosis
- Significant new diagnostic test results
- Change in causality based on new information
- Change in the event's outcome, including recovery
- Additional narrative information on the clinical course of the event

Investigators must also comply with local requirements for reporting serious adverse events to the local health authority and IRB/EC.

5.4.1 Medical Monitors and Emergency Medical Contacts

Contact Information for All Sites

To ensure the safety of study patients, an Emergency Medical Call Center will be available 24 hours per day, 7 days per week in case the above-listed contacts cannot be reached. The Emergency Medical Call Center will connect the investigator with an Emergency Medical Contact, provide medical translation service if necessary, and track all calls. Contact information, including toll-free numbers for the Emergency Medical Call Center, will be distributed to all investigators.

Ocrelizumab—F. Hoffmann-La Roche Ltd 81/Protocol MA30143, Version 10.0

5.4.2 Reporting Requirements for Serious Adverse Events and Adverse Events of Special Interest

5.4.2.1 Events That Occur prior to Study Drug Initiation

After informed consent has been obtained but prior to initiation of study drug, only serious adverse events caused by a protocol-mandated intervention should be reported. The paper Clinical Trial Serious Adverse Event/Adverse Event of Special Interest Reporting Form provided to investigators should be completed and submitted to the Sponsor or its designee immediately (i.e., no more than 24 hours after learning of the event), either by faxing or by scanning and emailing the form using the fax number or email address provided to investigators.

5.4.2.2 Events That Occur after Study Drug Initiation

After initiation of study drug, serious adverse events and adverse events of special interest will be reported until 48 weeks after the last dose of study drug. Investigators should record all case details that can be gathered immediately (i.e., within 24 hours after learning of the event) on the Adverse Event eCRF and submit the report via the electronic data capture (EDC) system. A report will be generated and sent to Roche Safety Risk Management by the EDC system

In the event that the EDC system is unavailable, the paper Clinical Trial Serious Adverse Event/Adverse Event of Special Interest Reporting Form provided to investigators should be completed and submitted to the Sponsor or its designee immediately (i.e., no more than 24 hours after learning of the event), either by faxing or by scanning and emailing the form using the fax number or email address provided to investigators. Once the EDC system is available, all information will need to be entered and submitted via the EDC system.

Instructions for reporting serious adverse events that occur after the end of the adverse event reporting period are provided in Section 5.6.

5.4.3 Reporting Requirements for Pregnancies

5.4.3.1 Pregnancies in Female Patients

Female patients of childbearing potential will be instructed *through the Informed Consent Form* to immediately inform the investigator if they become pregnant during the study. A paper Clinical Trial Pregnancy Reporting Form should be completed and submitted to the Sponsor or its designee immediately (i.e., no more than 24 hours after learning of the pregnancy), either by faxing or by scanning and emailing the form using the fax number or email address provided to investigators. Pregnancy should not be recorded on the Adverse Event eCRF. The investigator must withhold study drug for the duration of pregnancy and breastfeeding and counsel the patient, discussing the risks of the pregnancy and the possible effects on the fetus. Monitoring of the patient should continue until conclusion of the pregnancy. Any serious adverse events associated with the pregnancy (e.g., an event in the fetus, an event in the mother during or after the pregnancy, or a congenital anomaly/birth defect in the child) should be reported on the

Ocrelizumab—F. Hoffmann-La Roche Ltd 82/Protocol MA30143, Version 10.0

Adverse Event eCRF. In addition, the investigator will submit a Clinical Trial Pregnancy Reporting Form when updated information on the course and outcome of the pregnancy becomes available. Information about child heath up to 1 year should be collected on the infant health questionnaire (see Appendix 7).

Pregnancy: patients becoming pregnant by chance during the study will be withheld from ocrelizumab treatment but will remain in trial (patients will come at the clinic for the scheduled visits [wherever possible, adhering to the time of scheduled visits as per protocol] and will perform all assessments except MRI) and will have the opportunity to re-start ocrelizumab treatment after birth and breastfeeding are over. The total duration of treatment period will be 192 weeks from the date of first dose of ocrelizumab, irrespective of how long the treatment was interrupted due to pregnancy.

Patients who plan to become pregnant during the study will be withheld from ocrelizumab treatment and will follow the recommendations for contraception period after the last infusion with ocrelizumab for at least 6 months or longer in accordance with locally applicable ocrelizumab package leaflet. Upon discontinuation of study treatment, these patients will enter the safety follow-up period but will not restart the study treatment.

5.4.3.2 Abortions

A spontaneous abortion should be classified as a serious adverse event (as the Sponsor considers abortions to be medically significant), recorded on the Adverse Event eCRF, and reported to the Sponsor immediately (i.e., no more than 24 hours after learning of the event; see Section 5.4.2.).

If a therapeutic or elective abortion was performed because of an underlying maternal or embryofetal toxicity, the toxicity should be classified as a serious adverse event, recorded on the Adverse Event eCRF, and reported to the Sponsor immediately (i.e., no more than 24 hours after learning of the event; see Section 5.4.2). A therapeutic or elective abortion performed for reasons other than an underlying maternal or embryofetal toxicity is not considered an adverse event.

All abortions should be reported as pregnancy outcomes on the paper Clinical Trial Pregnancy Reporting Form.

5.4.3.3 Congenital Anomalies/Birth Defects

Any congenital anomaly/birth defect in a child born to a female patient exposed to study drug should be classified as a serious adverse event, recorded on the Adverse Event eCRF, and reported to the Sponsor immediately (i.e., no more than 24 hours after learning of the event; see Section 5.4.2.).

5.5 FOLLOW-UP OF PATIENTS AFTER ADVERSE EVENTS

5.5.1 Investigator Follow-Up

The investigator should follow each adverse event until the event has resolved to baseline grade or better, the event is assessed as stable by the investigator, the patient is lost to follow-up, or the patient withdraws consent. Every effort should be made to follow all serious adverse events considered to be related to study drug or trial-related procedures until a final outcome can be reported.

During the *adverse event reporting* period (*defined in Section* 5.3.1), resolution of adverse events (with dates) should be documented on the Adverse Event eCRF and in the patient's medical record to facilitate source data verification.

All pregnancies reported during the study should be followed with a Pregnancy Outcome and Infant Health Information on First Year of life questionnaire provided by the Sponsor.

5.5.2 Sponsor Follow-Up

For serious adverse events, adverse events of special interest, and pregnancies, the Sponsor or a designee may follow up by telephone, fax, electronic mail, and/or a monitoring visit to obtain additional case details and outcome information (e.g., from hospital discharge summaries, consultant reports, autopsy reports) in order to perform an independent medical assessment of the reported case.

5.6 ADVERSE EVENTS THAT OCCUR AFTER THE ADVERSE EVENT REPORTING PERIOD

The Sponsor should be notified if the investigator becomes aware of any serious adverse event that occurs after the end of the adverse event reporting period (defined as 48 weeks after the last dose of study drug), if the event is believed to be related to prior *exposure to* study drug. These events should be reported through use of the Adverse Event eCRF. However, if the EDC system is not available, the investigator should report these events directly to the Sponsor or its designee, either by faxing or by scanning and emailing the paper Clinical Trial Serious Adverse Event/Adverse Event of Special Interest Reporting Form using the fax number or email address provided to investigators.

5.7 EXPEDITED REPORTING TO HEALTH AUTHORITIES, INVESTIGATORS, INSTITUTIONAL REVIEW BOARDS, AND ETHICS COMMITTEES

The Sponsor will promptly evaluate all serious adverse events and adverse events of special interest against cumulative product experience to identify and expeditiously communicate possible new safety findings to investigators, IRBs, and applicable health authorities based on applicable legislation.

To determine reporting requirements for single adverse event cases, the Sponsor will assess the expectedness of these events using the reference safety information in the following document:

Ocrelizumab IB

The Sponsor will compare the severity of each event and the cumulative event frequency reported for the study with the severity and frequency reported in the applicable reference document.

Reporting requirements will also be based on the investigator's assessment of causality and seriousness, with allowance for upgrading by the Sponsor as needed.

Certain adverse events are anticipated to occur in the study population at some frequency independent of study drug exposure and will be excluded from expedited reporting.

6. STATISTICAL CONSIDERATIONS AND ANALYSIS PLAN

The analysis of this open label, single arm study will be descriptive and primarily based on descriptive statistical methods. Unless otherwise specified, statistical tests will be exploratory in nature. Corresponding 95% CIs will be presented as appropriate. No correction for multiple testing will be applied.

Full details of all statistical aspects and planned statistical analyses will be specified in a separate Statistical Analysis Plan (SAP), which will be finalized prior to the locking of the study database and may include further exploratory analyses not explicitly described in this section, as well as analyses of data from the study phase beyond the main 192week study period, e.g., safety follow-up information.

Analysis populations

The primary effectiveness and safety analyses will be performed using the intent-to-treat (ITT) population. The per-protocol (PP) population will be used for supportive effectiveness analyses of selected effectiveness endpoints in order to evaluate the influence of major protocol violators on key effectiveness endpoints.

ITT Population

All enrolled patients who received any dose of ocrelizumab will be included in the ITT population. Patients who prematurely withdrew from the study for any reason will still be included in the ITT population.

PP Population

The PP population will include all ITT patients without protocol deviations deemed to affect the assessment of effectiveness. The list of criteria leading to exclusion from the PP population will be finalized prior to database closure and documented in the SAP.

Ocrelizumab—F. Hoffmann-La Roche Ltd

85/Protocol MA30143, Version 10.0

Safety Population

The safety population will include all enrolled patients who received any dose or part of a dose of ocrelizumab.

6.1 DETERMINATION OF SAMPLE SIZE

The main study is a single-arm effectiveness and safety study. There is no formal statistical hypothesis and all analyses will be descriptive. The results for the key endpoints will be presented in a descriptive analysis including the corresponding 95% the confidence intervals.

Sample size considerations for the main study are based on pooled data from two ocrelizumab phase III trials in RRMS (OPERA I and II). Based on extrapolations from these studies, we can conservatively expect 15% of patients (or less) to have a CDP event and approximately the same number of patients to be prematurely withdrawn and censored before week 192.

In this case, for 1,100 patients, the precision (half-width of the 95% confidence interval) of the estimated CDP rate by study end is expected to be approximately 1.8%, i.e., the 95% confidence interval of (13.2%, 16.8%).

In OPERA the EDSS improvement at 2 years had a standard deviation of 0.74, based on 240 patients from the ocrelizumab group, who were previously treatment-naïve with disease duration \leq 3 years and EDSS \leq 3.5. The standard deviation was rather stable over time and is assumed to remain stable after four years of treatment. A sample size of 1,100 patients is expected to provide a precision for the estimate of the EDSS change from baseline of about 0.037, assuming a standard deviation of 0.75. Assuming no EDSS change from baseline, the 95% confidence interval is expected to be (-0.074, 0.074).

The main study was initially planned to enroll at least 600 patients. Approximately 550 additional patients were to be enrolled in the shorter infusion sub-study. They would also be enrolled in the main study (see Appendix 10 for more details). Therefore, the main study would enroll a total of at least 1,100 patients. A total of 1,225 patients (678 in the main study and 547 in the shorter infusion substudy) were enrolled in the study.

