Sample size considerations for the main study are based on pooled data from two ocrelizumab phase III trials in RRMS (OPERA I and II). Based on extrapolations from these studies, we can conservatively expect 15% of patients (or less) to have a CDP event and approximately the same number of patients to be censored (including the patients who drop out during the study) by week 192. In this case, for 1,100 patients, the precision (half-width of the 95% confidence interval) of the estimated CDP rate by study end is expected to be approximately 1.8% i.e., the 95% confidence interval will be (13.2%, 16.8%). In OPERA the EDSS improvement at 2 years had a standard deviation of 0.74, based on 240 patients from the ocrelizumab group, who were previously treatment-naïve with disease duration \leq 3 years and EDSS \leq 3.5. The standard deviation was rather stable over time and is assumed to remain stable after four years of treatment. A sample size of 1,100 patients is expected to provide a precision for the estimate of the EDSS change from baseline of about 0.037, assuming a standard deviation of 0.75. Assuming no EDSS change from baseline to week 196, with 1,100 patients, the 95% confidence interval will be (-0.074, 0.074).

The main study was initially planned to enroll at least 600 patients. Approximately 550 additional patients were to be enrolled in the shorter infusion substudy. They would also be enrolled in the main study (see Appendix 10 for more details). Therefore, the main study would enroll a total of at least 1,100 patients. A total of 1,225 patients (678 in the main study and 547 in the shorter infusion substudy) were enrolled in the study.

Interim Analyses

Exploratory analyses of selected endpoints (including CDP and safety analysis) will be performed during the course of the study, for example, after all patients have completed the first 48 weeks of the treatment phase and the necessary data are available.

LIST OF ABBREVIATIONS AND DEFINITIONS OF TERMS

Abbreviation	Definition
ADA	Anti-drug antibodies
AE	Adverse event
AIDS	Acquire immunodeficiency syndrome
ALT	Alanine aminotransferase
ANC	Absolute neutrophil count
ARR	Annual relapse rate
AST	Aspartate aminotransferase
β-hCG	Beta subunit human chorionic gonadotropin
BICAMS	Brief International Cognitive Assessment for Multiple Sclerosis
BRC	Biological Resource center
BVMT-R	Brief Visuospatial Memory Test Revised
CCOD	Clinical cut-off date
CDI	Confirmed disability improvement

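### The 95% precision figures given for 1,100 patients are miscalculated: CDP half-width is 2.1 points, not 1.8, and EDSS is ±0.044, not 0.037 or ±0.074

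*Protocol*

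**What the plan says.** Protocol Section 6.1 (Determination of Sample Size) assumes that "we can conservatively expect 15% of patients (or less) to have a CDP event", with "approximately the same number of patients to be prematurely withdrawn and censored before week 192". For 1,100 patients it states that "the precision (half-width of the 95% confidence interval) of the estimated CDP rate by study end is expected to be approximately 1.8"%, and gives "the 95% confidence interval of (13.2%, 16.8"%).

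For EDSS change the same section promises "a precision for the estimate of the EDSS change from baseline of about 0.037, assuming a standard deviation of 0.75". It then adds that, if there is no change, "the 95% confidence interval is expected to be (-0.074, 0.074"). The synopsis carries the same figures and ties the EDSS interval explicitly to the sample size: "with 1,100 patients, the 95% confidence interval will be (-0.074, 0.074").

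No confidence level other than 95% is mentioned. Section 6 says that 95% intervals will be presented.

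**The concern.** Section 6.1 defines precision as the half-width of a 95% interval, yet the figures do not follow from the stated rate, SD and sample size. The two EDSS figures also disagree with each other: an interval centred on zero with half-width 0.037 would be (-0.037, 0.037), not (-0.074, 0.074).

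The main study is single-arm and descriptive, with no formal hypothesis (Section 6.1) and no primary endpoint (Section 6.4.1). There is no power calculation, so these precision figures are its only quantitative account of what the sample size achieves. At the assumed rate and SD, the 95% intervals in the study report would not match the planned ones. A reader could wrongly put that down to dropout or extra variability.

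**Working it through.** **Inputs** (Protocol Section 6.1): n = 1,100; CDP rate p = 0.15; SD of EDSS change = 0.75; about 15% censored before week 192; 1,225 actually enrolled.

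**CDP.** Standard error = √(0.15 × 0.85 / 1,100) = 0.01077.

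- Reproducing the plan: 1.645 × 0.01077 = 0.0177, which rounds to the stated 1.8%. This is a 90% multiplier; 1.8% implies a level of about 90.5%.
- At 95%: 1.96 × 0.01077 = 0.0211, interval (12.9%, 17.1%).
- Other 95% methods do not give (13.2%, 16.8%): Wilson gives (13.0%, 17.2%) and Clopper-Pearson (12.9%, 17.2%).
- n for a true 1.8%: 1.96² × 0.1275 / 0.018² ≈ 1,512.
- At the 1,225 enrolled: 1.96 × √(0.1275 / 1,225) = 0.0200.
- Censoring only widens the interval. Simulated Kaplan-Meier half-widths with about 15% censored were 2.1 to 2.3 points, depending on the assumed timing of events and dropout, which the protocol does not give. Counting only 85% of patients (n = 935) gives 2.29.

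**EDSS.** Standard error = 0.75 / √1,100 = 0.0226.

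- Reproducing the plan: 1.645 × 0.0226 = 0.0372, matching the stated 0.037; and 2 × 0.037 = 0.074, matching the stated interval limits.
- At 95%: 1.96 × 0.0226 = 0.0443, interval (-0.044, 0.044).
- 0.037 / 0.0443 = 0.84, so the stated precision is about 16% too narrow. 0.074 / 0.0443 = 1.67, so the stated interval is about 67% too wide.
- n for ±0.074 at 95%: (1.96 × 0.75 / 0.074)² ≈ 395. n for ±0.037 at 95%: (1.96 × 0.75 / 0.037)² ≈ 1,579.
- At 1,225: 1.96 × 0.75 / 35 = 0.042.

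**Comparison with the rest of the protocol.** The multiplier 1.96 is used correctly elsewhere. Appendix 8 gives 13.9% for a proportion of 50% with n = 50, and 1.96 × √(0.25 / 50) = 0.139. Appendix 10, Table 4 gives ±5.1 points at 12.4% in both arms, and 1.96 × √(2 × 0.124 × 0.876 / 325) = 0.051. Section 6.1 of the main protocol is the exception.

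**The case against.** Five points can be made for the plan.

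- **Origin of 1,100.** It comes from at least 600 patients originally planned plus about 550 added for the shorter infusion substudy, which has its own rationale. It was not derived from a precision target. This stands: the figures describe what 1,100 delivers and did not generate it. They remain the main study's only quantitative support for that number.
- **Consequence.** Enrolment is complete at 1,225, no decision rule uses these figures, and the reported intervals will come from the data. The CDP error is about 0.3 points. This also stands and limits the harm, but the statements are still wrong.
- **Mechanism.** No document mentions 90% or 1.645. The match holds after rounding, so the explanation is an inference. The mismatch with 95% does not depend on it.
- **Meaning of precision for EDSS.** The 95% definition is attached to the CDP sentence only. If 0.037 were a standard error, ±0.074 would be about two standard errors and the two figures would agree with each other. But a standard error of 0.037 needs (0.75 / 0.037)² ≈ 411 patients; at 1,100 it is 0.023. The figures are wrong on either reading.
- **The allowance for a rate below 15%.** A 1.8-point half-width at 95% needs a rate of about 10.3%, but the printed interval is centred on 15%.

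**Conclusion.** The concern holds. On the plan's own inputs, none of its CDP or EDSS precision figures is correct at 95% in either Section 6.1 or the synopsis. The CDP half-width is 2.11 points against 1.8 stated, so the plan claims more precision than it has. The EDSS half-width is 0.044, against a stated precision of 0.037 (too narrow) and a stated interval of ±0.074 (too wide), so the EDSS text errs in both directions.

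These results assume the plan's rate, SD and full sample of 1,100, and normal-approximation intervals. Enrolment of 1,225 does not rescue the CDP figure (2.0 points), and censoring makes it worse. The SAP provided covers only the shorter infusion substudy and does not correct the figures; whether a main-study SAP does so cannot be seen. The design is unaffected.

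**What to change.** Restate the figures in Section 6.1 and in the synopsis, and define precision as the 95% half-width for both endpoints:

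- **CDP:** half-width about 2.1 percentage points, (12.9%, 17.1%), for 1,100 patients. Add that with about 15% early censoring it is about 2.2, range 2.1 to 2.3, depending on the assumed timing of events and dropout.
- **EDSS change:** half-width about 0.044, (-0.044, 0.044), for 1,100 patients. Treat dropout in the same way as for CDP: if 15% have no final value (n = 935), it is about 0.048.
- **For the 1,225 enrolled, alongside:** 2.0 points and 0.042 before any allowance for dropout.

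If a protocol amendment for this alone is disproportionate, put the corrected figures in the main-study SAP, which Section 6 says will be finalised before database lock. The cost is a text correction and a slightly less favourable CDP precision statement.
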